### **3.4. Rationale for Flat Dosing of Nivolumab Monotherapy**

Nivolumab monotherapy has been extensively studied in a number of tumor types including NSCLC, melanoma, RCC, and CRC with body weight normalized dosing (mg/kg). Nivolumab pharmacokinetics (PK) and exposures of subjects in these studies have been characterized by population pharmacokinetic (PPK) analysis of data collected these studies, together with PK data from several phase 1, 2, and 3 clinical studies of nivolumab monotherapy in solid tumors. Population PK (PPK) analyses have shown that the PK of nivolumab are linear, with dose proportional exposures over a dose range of 0.1 mg/kg to 10 mg/kg, and are similar across tumor types. Nivolumab clearance and volume of distribution were found to increase with increasing body weight, but the increase was less than proportional, indicating that a mg/kg dose represents an over-adjustment for the effect of body weight on nivolumab PK. Given the relationship between nivolumab PK and body weight, a flat dose is expected to lead to lower exposures in heavier patients, relative to the exposures in lighter patients.

[figure not shown]
Using the PPK model, nivolumab steady-state trough, peak and time-averaged concentration ( $C_{minss}$ ,  $C_{maxss}$ , and  $C_{avgss}$ , respectively) were predicted for a flat nivolumab dose of 240 mg Q2W and compared to those following administration of 3 mg/kg Q2W in NSCLC subjects. A dose of 240 mg nivolumab is identical to a dose of 3 mg/kg for subjects weighing 80 kg, which is the approximate median body weight of NSCLC subjects in the 3 Phase 2 and 3 BMS clinical studies of nivolumab monotherapy. The geometric mean values of  $C_{minss}$ ,  $C_{maxss}$ , and  $C_{avgss}$  with flat dosing are slightly (< 15%) higher than that produced by a 3 mg/kg dose, and the coefficient of variation (cv%) in these measures of exposure are only slightly (< 10%) greater than that of 3 mg/kg dosing.

Across the various tumor types in the BMS clinical program, nivolumab has been shown to be safe and well tolerated up to a dose level of 10 mg/kg, and the relationship between nivolumab exposure produced by 3 mg/kg and efficacy has been found to be relatively flat. Taken together, the PK, safety, and efficacy data indicate that the safety and efficacy profile of 240 mg nivolumab will be similar to that of 3 mg/kg nivolumab.

### **3.5. Rationale for Using Major Histocompatibility Class II (MHC-II) for Treatment Stratification**

[figure not shown]
MHC-II expression is typically restricted to professional antigen presenting cells such as dendritic cells. In this context, these molecules present antigens to CD4+ Helper T cells to promote immune responses. By contrast, MHC class I molecules are ubiquitous across all nucleated cell types, present antigens to cytotoxic, CD8+ T cells. Given the known critical role of tumor cell killing by cytotoxic T cells, most studies historically have examined the role of MHC-I in tumors as opposed to MHC-II.

It has been well known, however, that a subset of tumors across the cancer spectrum expresses MHC-II, although the mechanism of this finding has not been well-understood. We observed that MHC-II expression in breast cancer correlated with T cell infiltration and improved clinical outcomes compared to MHC-II negative tumors. More importantly, we published a strong correlation between MHC-II expression and response to anti-PD-1 monotherapy (**Figure 1**). In discovery and validation cohorts, response rates were improved in the MHC-II populations (79% and 75% vs. 38% and 27%; p=0.01 and 0.03, respectively). PFS and OS were also superior in the MHC-II expressors (median PFS not reached vs. 3.2 months, p=0.02); median OS not reached vs. 27.5 months, p = 0.003). In addition, expression of MHC-II strongly correlated with improved outcomes in Hodgkin lymphoma patients treated with nivolumab. An additional independent cohort using multiparameter immunofluorescence assessment also demonstrated improved clinical outcomes in patients with high expression of MHC-II. Thus, multiple independent cohorts have confirmed the benefits of anti-PD-1 therapy in tumors with high expression of MHC-II.

**Figure 1:** MHC-II positivity and response in (A) discovery and (B) validation cohort. Example of response in MHC-II+ patient (C). (D) Progression free and overall survival in combined cohort by MHC-II expression. (E) Correlation matrix of IHC markers. P values for the Pearson's correlation appear above the diagonal and correlation coefficients ( $r$ ) appear below the diagonal.

We performed several studies to explain this finding mechanistically. MHC-II positive cell lines were enriched for gene signatures including the previously defined “PD-1 signaling,” “allograft rejection,” and “T cell receptor signaling.” Importantly, MHC-II positive tumors were also highly infiltrated with CD4+ and CD8+ T cells. Gene expression signatures for MHC-II positive tumors were also enriched with interferon- $\gamma$  gene signatures and immune checkpoint molecules. To understand the functional role of MHC-II, we enforced the master regulator of MHC-II expression, CIITA in a murine cancer model. Notably, enforced CIITA tumors were rejected by the mice at a higher rate than control tumors (**Figure 2A**). Those that did establish had higher immune cell infiltrate with both CD4+ and CD8+ T cells. Importantly, LAG3, a cognate antigen and antagonist of MHC-II, was also highly expressed in the MHC-II expressing mouse tumors as well (**Figure 2B**). Increased expression of LAG-3 was also observed in human melanomas that developed acquired resistance to anti-PD-1 (**Figure 2C**). Combination blockade of LAG-3 and PD-1 was particularly active in this subpopulation, suggesting that LAG-3 may counteract the pro-immune effects of MHC-II (**Figure 2D**). This suggests that 1) MHC-II plays a functional role in anti-PD-1 mediated T cell rejection of tumors; 2) LAG-3 mediates resistance to anti-PD-1, at least in part; and 3) Co-targeting MHC-II positive tumors by LAG-3 and PD-1 blockade may be synergistic.

**Figure 2:** (A) Tumor growth of MHC-II negative (pMX-puro) or MHC-II positive (pMX-Ciita) MMTV-neu tumors in mouse models, showing increased rejection for MHC-II positive. (B) LAG-3 expression in MHC-II positive vs. negative tumors. (C) LAG-3+ tumor infiltrating lymphocytes at baseline, and after acquired resistance to anti-PD-1 therapy, demonstrating that LAG-3 expression is increased at resistance. Treatment with IgG (placebo), anti-PD-1, and anti-LAG-3 in MHC-II positive (Ciita) and MHC-II negative (Puro), demonstrating high response rates for combination treatment in MHC-II positive mouse tumors (pink line).

By contrast, MHC-II non-expressing tumors have less evidence of adaptive immunity and T cell infiltration, particularly CD4+ T cells. Thus, we hypothesize that the combination of ipilimumab and nivolumab will augment CD4+ T cell help and overcome the limitations of PD-1 targeting alone.

### **3.6. Rationale for Permitting Continued Treatment in Select Cases of Progressive Disease**

Accumulating clinical evidence indicates some subjects treated with immune system stimulating agents may develop progression of disease (by conventional response criteria) before demonstrating clinical objective responses and/or stable disease. This phenomenon was observed in up to 10% of patients treated with nivolumab or pembrolizumab, and also with ipilimumab monotherapy. Two hypotheses have been put forth to explain this phenomenon. First, enhanced inflammation within tumors could lead to an increase in tumor size which would appear as enlarged index lesions and as newly visible small non-index lesions. Over time, both the malignant and inflammatory portions of the mass may then decrease leading to overt signs of clinical improvement. Alternatively, in some individuals, the kinetics of tumor growth may initially outpace anti-tumor immune activity. With sufficient time, the anti-tumor activity will dominate and become clinically apparent. Therefore, subjects will be allowed to continue study therapy after initial investigator-assessed RECIST 1.1 defined progression if they are assessed to be deriving clinical benefit and tolerating study drug (Section 9.8). Such subjects must discontinue study therapy upon evidence of further progression.

### **3.7. Rationale for Primary Endpoint**

The primary endpoint for this study is change in CD8+ T cell infiltration. Several studies have demonstrated influx of CD8+ T cells as demonstrating immunologic recognition and targeting, and as an early surrogate for treatment response. For example, one study demonstrated that expression of CD8 in early on-treatment biopsies was completely non-overlapping in responders compared with non-responders. Thus, this metric can serve as an accurate surrogate of immunologic recognition and tumor responses, and is likely more reliable than a metric such as complete pathologic response, particularly in the setting of bulky tumors that may require additional time for complete regression. In addition, in this signal finding phase II study, we are evaluating two arms with likely active treatments in parallel, rather than comparing these interventions. Sample size is further based on doubling of CD8+ T cell infiltration from analysis of responding patients in two studies, with a standard deviation of 1000.

### **3.8. Research Hypotheses**

Patients with MHC-II expressing melanomas will have high rates of change in activated GZMB+ CD8+ T-cell density intratumorally with nivolumab and relatlimab therapy; MHC-II expression is an effective stratifying marker in melanoma that can be used in future studies to select optimal treatment.

## **4. OBJECTIVES AND ENDPOINTS**

Objectives	Endpoints

Primary
 

• To evaluate the efficacy, measured by change in activated GZMB+ CD8+ T-cell density intratumorally, of two immunotherapy regimens in patients with advanced melanoma: nivolumab plus relatlimab in patients with MHC-II (+) melanoma; and nivolumab plus ipilimumab in patients with MHC-II (-) melanoma.

	

• Change in activated GZMB+ CD8+ T-cell density intratumorally.

Secondary
 

• To evaluate the response rate, median progression free survival, overall survival, and safety and tolerability of nivolumab and relatlimab in patients with MHC-II (+) melanoma; and of nivolumab plus ipilimumab in patients with MHC-II (-) melanoma.

	

• Response rate (RR)

• Median progression free survival (mPFS)

• Median overall survival (mOS)

• Adverse events, clinical laboratory values, vital signs, ECGs, and other safety biomarkers.

Exploratory
 

• To explore potential associations of biomarkers with clinical efficacy and/or incidence of adverse events due to study drug by analyzing biomarker measures within the peripheral blood and tumor microenvironment.

	

• Automatic quantitative analysis (AWUA), single cell RNA sequencing, mass cytometry, T-cell receptor sequencing, germline DNA/HLA haplotyping.

## **5. PATIENT SELECTION**

Questions regarding patient eligibility must be addressed and resolved by the investigator in consultation with the sponsor-investigator or designee prior to enrollment.

### **5.1. Inclusion Criteria**

Patients must meet all of the following inclusion criteria to be eligible for enrollment into the study:

1. Signed and dated written informed consent.
2.  $\geq 18$  years of age at the time of informed consent.
3. Eastern Cooperative Oncology Group (ECOG) performance status of 0 or 1.
4. Histologically confirmed locally advanced/unresectable or metastatic melanoma.
5. Patients who have received prior anti-CTLA-4 or anti-PD-1/PD-L1 for adjuvant treatment of melanoma are eligible if  $> 6$  months have elapsed between the last dose of adjuvant treatment and starting this study – provided there is no history of life-threatening toxicity related to such prior treatment, or such toxicity is unlikely to re-occur with standard countermeasures (e.g. hormone replacement after endocrinopathy).
6. Patients who have received adjuvant therapy with interferon and/or a BRAF inhibitor and/or MEK inhibitor for adjuvant therapy are permitted to enroll.
7. At least one measurable target lesion as defined by RECIST 1.1 which can be followed by CT or MRI.
  - If located in a previously irradiated area, a tumor lesion is considered a measurable/target lesion only if subsequent disease progression in the lesion has been documented at least 90 days following completion of radiotherapy.
8. Adequate organ and bone marrow function  $\leq 14$  days prior to first dose of protocol-indicated treatment:
  - White blood cell count (WBC)  $\geq 2,000/\text{mm}^3$ .
  - Absolute neutrophil count (ANC)  $\geq 1,500/\text{mm}^3$ .
  - Platelets  $\geq 75,000/\text{mm}^3$ .
  - Hemoglobin  $\geq 8.0 \text{ g/dL}$ .
  - Serum creatinine  $\leq 2.0x$  upper limit of normal (ULN), or calculated creatinine clearance (CrCl)  $> 40 \text{ mL/min}$  per the Cockcroft-Gault formula ([Appendix 1](#)).
  - Total bilirubin  $\leq 1.5x$  ULN  
(except patients with Gilbert Syndrome, who must have total bilirubin  $< 3.0 \text{ mg/dL}$ ).
  - AST (aspartate aminotransferase) and ALT (alanine aminotransferase)  $\leq 3.0x$  ULN ( $\leq 5.0x$  ULN in those with hepatic metastases).

9. Acceptable troponin level  $\leq$  14 days prior to first dose of protocol-indicated treatment:
  - Troponin T (TnT) or I (TnI)  $\leq$  2 $\times$  institutional ULN.
  - Subjects with TnT or TnI levels between >1 to 2 $\times$  ULN will be permitted if repeat levels within 24 hours are  $\leq$  1 $\times$  ULN.
  - If TnT or TnI levels are >1 to 2 $\times$  ULN within 24 hours, the subject may undergo a cardiac evaluation and be considered for treatment based on the discretion of the PI.
  - When repeat levels within 24 hours are not available, a repeat test should be conducted as soon as possible.
  - If TnT or TnI repeat levels beyond 24 hours are < 2 $\times$  ULN, the subject may undergo a cardiac evaluation and be considered for treatment, based on the discretion of the PI.
10. Arm A: Corrected QT interval (QTc) by Fridericia's method (QTcF) assessed by electrocardiogram (ECG) completed  $\leq$  28 days before initiation of protocol treatment ([Section 8.9](#)), and resulted as:
  - QTcF  $\leq$  480 msec
11. Tumor tissue from a biopsy or resection obtained since completion of the last systemic therapy must be available for analysis of MHC-II status and for biomarker analysis. If a sample is not available or if the quantity or quality of tissue is insufficient to provide adequate results, an additional biopsy may be performed for MHC-II analysis. Patients cannot be enrolled on the study unless MHC-II is known.
12. Women must not be breastfeeding.
13. A woman of childbearing potential (WOCBP) – see Appendix 4 for definition of WOCBP – must have a negative serum pregnancy test within 14 days prior to receiving first dose of protocol-indicated treatment, and must agree to follow instructions for using acceptable contraception ([Appendix 4](#)) from the time of signing consent, and for 165 days (24 weeks) after her last dose of protocol-indicated treatment.
14. A man able to father children (see Appendix 4 for definition) who is sexually active with a WOCBP must agree to follow instructions for using acceptable contraception ([Appendix 4](#)), from the time of signing consent, and for 225 days (33 weeks) after his last dose of protocol-indicated treatment.

## **5.2. Exclusion Criteria**

Patients meeting any of the following criteria will not be permitted to enter the trial:

1. Patients with uveal melanoma.
2. Prior systemic anticancer therapy for unresectable or metastatic melanoma.
3. Prior treatment with LAG-3 targeted agents.
4. Subjects with active, known, or suspected autoimmune disease. Subjects with type I diabetes mellitus, hypothyroidism only requiring hormone replacement, skin disorders (such as vitiligo, psoriasis or alopecia) not requiring systemic treatment, or conditions not expected to recur in the absence of an external trigger are permitted to enroll.

5. Uncontrolled or significant cardiovascular disease including, but not limited to, any of the following:
  - Myocardial infarction (MI) or stroke/transient ischemic attack (TIA) within the 6 months prior to consent.
  - Uncontrolled angina within the 3 months prior to consent.
  - Any history of clinically significant arrhythmias (such as ventricular tachycardia, ventricular fibrillation, torsades de pointes, or poorly controlled atrial fibrillation).
  - QTc prolongation > 480 msec.
  - History of other clinically significant cardiovascular disease (i.e., cardiomyopathy, congestive heart failure with New York Heart Association [NYHA] functional classification III-IV, pericarditis, significant pericardial effusion, significant coronary stent occlusion, poorly controlled deep venous thrombosis, etc.).
  - Cardiovascular disease-related requirement for daily supplemental oxygen.
  - History of two or more myocardial infarctions or two or more coronary revascularization procedures within the past 3 years.
  - Subjects with history of myocarditis, regardless of etiology.
6. A confirmed history of encephalitis, meningitis, or uncontrolled seizures in the year prior to informed consent.
7. Participants with a condition requiring systemic treatment with either corticosteroids (>10 mg daily prednisone or equivalent) or other immunosuppressive medications within 14 days of enrollment. Inhaled or topical steroids, and adrenal replacement steroid doses >10 mg daily prednisone or equivalent, are permitted in the absence of active autoimmune disease.
8. Subjects with active central nervous system (CNS) metastases, active brain metastases or leptomeningeal metastatic foci. For the subjects with brain metastases, if they are asymptomatic, they are eligible to participate in this study. If participants have received treatment for brain metastases and have no clinical evidence of progressive disease at least 1 week after completion of treatment for brain metastases and within 28 days prior to the first dose of protocol-indicated treatment on this study, they are eligible to participate in this study.
9. Known history of testing positive for human immunodeficiency virus (HIV) or known acquired immunodeficiency syndrome (AIDS).
10. Known history of hepatitis B or hepatitis C.
11. Any significant medical condition, laboratory abnormality, or psychiatric illness, that would prevent the subject from participating in the study or place the subject at unacceptable risk if he/she were to participate in the study, or any condition that confounds the ability to interpret data from the study.
12. Subjects with life expectancy < 6 months.
13. Subjects receiving any other investigational or standard antineoplastic agents.

---

- 14. Prior malignancy active within the previous 3 years currently requiring treatment except for locally curable cancers that have been apparently cured, such as basal or squamous cell skin cancer, superficial bladder cancer, or carcinoma in situ of the prostate, cervix, or breast.
- 15. Prisoners or participants who are involuntarily incarcerated.
- 16. Participants who are compulsorily detained for treatment of either a psychiatric or physical (e.g. infectious disease) illness.
- 17. Psychological, familial, sociological, or geographical conditions that potentially hamper compliance with the study protocol and follow-up schedule; those conditions should be discussed with the participant before registration in the trial.

### **5.3. Inclusion of Underrepresented Populations**

Women and men of all races and ethnic groups are eligible for this trial. There is no bias towards gender, age, or race in the clinical trial outlined.

### **5.4. Number of Patients and Replacement of Patients Who Discontinue Early**

Approximately 36 evaluable patients with advanced melanoma are anticipated to enroll in this study at Vanderbilt University Medical Center and approximately two additional academic medical centers in the U.S.

In general, it intended that patients will be treated until confirmed disease progression or intolerable toxicity. The criteria for patient discontinuation are listed in [Section 9.9](#).

If a patient discontinues protocol treatment in the first cycle for reasons clearly not related to protocol treatment after completing fewer than 1 planned cycle of study therapy, then that patient will be considered not evaluable for toxicity and will be replaced with a new patient.

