## 1. SYNOPSIS

Trial Title	A Phase II Two-Arm Open-Label Study of Nivolumab plus Relatlimab or Ipilimumab in Metastatic Melanoma Stratified by MHC-II Expression.
Trial Sites	Vanderbilt University Medical Center and approximately 2 additional academic medical centers in the United States.
Overall Design	This is an open-label, non-randomized two arm Phase 2 study of intravenous nivolumab plus intravenous ipilimumab or intravenous relatlimab in patients with metastatic melanoma stratified by MHC-II expression.
Hypothesis	Patients with MHC-II expressing melanomas will have high rates of change in activated GZMB+ CD8+ T-cell density intratumorally with nivolumab and relatlimab therapy; MHC-II expression is an effective stratifying marker in melanoma that can be used in future studies to select optimal treatment.
Study Design	
Patients will be stratified into 2 arms: Arm A: MHC-II positive patients, and Arm B: MHC-II negative patients.
 
Arm A: Treatment will consist of cycles lasting 28 days (4 weeks) per cycle (nivolumab + relatlimab):
 
 
• On Day 1 of each 28-day cycle, all patients are scheduled to receive nivolumab and relatlimab intravenously.
 
 
Arm B: Treatment will consist of four initial cycles lasting 21 days (3 weeks) per cycle (nivolumab + ipilimumab); followed by cycles lasting 28 days (4 weeks) for nivolumab monotherapy:
 
 
• On Day 1 of cycles 1-4, all patients are scheduled to receive ipilimumab and nivolumab intravenously.
 
 
Starting with cycle 5, patients will receive nivolumab intravenously every 4 weeks.

Duration of Treatment	It is intended that patients will be treated until RECIST 1.1 confirmed disease progression, until intolerable toxicity, or up to a maximum of 2 years after initiation of study treatment.

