### **18.2. Sample Size and Power**

The primary endpoint for this study is change in GZMB+ CD8+ T cell infiltration. A total sample size of 36 with 18 in each arm will provide 83% power to detect a difference in mean activated CD8+ T cell density change of one standard deviations (e.g., 1 SD=1000 counts/mm^2 is roughly the effect size for doubling T cell count), with a two-sided significance level of 0.05. Assuming a 10% dropout rate, a total number of 40 patients is planned for enrollment in the study to ensure the study has adequate statistical power for the primary analysis.

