### **18.3. Secondary Endpoints**

Efficacy for each arm: response rate as measured by RECIST 1.1, progression free survival, and overall survival. Survival statistics will be assessed descriptively for each arm and summarized with median, 1 year, and 2 year landmark analyses.

Safety: safety and tolerability of nivolumab plus relatlimab in patients with MHC-II (+) melanoma, and of nivolumab plus ipilimumab in patients with MHC-II (-) melanoma.

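### Section 5.4 makes some dosed patients who stop in cycle 1 not evaluable for toxicity, and no safety population restores them, so the toxicity rates can be biased in either direction

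*Combined protocol and SAP*

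**What the plan says.** Section 5.4 concerns a patient who "discontinues protocol treatment in the first cycle for reasons clearly not related to protocol treatment after completing fewer than 1 planned cycle of study therapy". Such a patient "will be considered not evaluable for toxicity and will be replaced with a new patient".

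Section 6 cancels the registration of anyone who does not receive therapy in the allowed time. The 5.4 rule therefore concerns people who have been dosed. Sections 2.2 and 9.1 place both drugs of each regimen on Day 1 of the cycle, so a cycle 1 leaver may already have had the full cycle 1 treatment. The synopsis states: "This is an open-label, non-randomized two arm Phase 2 study". No section assigns the judgement about the reason for stopping to an independent reviewer.

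Safety is a secondary endpoint. Section 18.3 lists "Safety: safety and tolerability of nivolumab plus relatlimab in patients with MHC-II (+) melanoma" and the same for the other arm. Neither 18.3 nor 18.4 gives a safety population or denominator. Section 13.1 collects non-serious events from first dose until 100 days after the last dose or the start of another anticancer therapy. For new non-serious events in the 30-day follow-up it narrows this to events with a reasonable possibility of being drug-related. Serious events are reported to 100 days regardless of causality. Replaced patients are not exempted.

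On numbers, Section 5.4 says "Approximately 36 evaluable patients with advanced melanoma are anticipated to enroll in this study". Section 18.2 says "A total sample size of 36 with 18 in each arm will provide 83% power" for a difference in "mean activated CD8+ T cell density change of one standard deviations", "with a two-sided significance level of 0.05", and raises enrolment to 40 for 10% dropout. Section 2 closes an arm once 18 have enrolled. The on-treatment biopsy is at Cycle 2 Day 15 in Arm A and Cycle 3 Day 1 in Arm B (Section 8.13).

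**The concern.** A toxicity rate describes what happens to people who are exposed, so anyone exposed belongs in the denominator. Section 5.4 takes some of them out after dosing, on a judgement by staff who know the treatment. The test is the reason for stopping, not whether the patient had toxicity. A patient who leaves for an unrelated reason but had a drug-related event in cycle 1, or has one afterwards, still meets the rule. Even without any misattribution, observed toxicity can therefore be left out of the summary. With about 18 patients per arm, one or two exclusions are visible in the percentages.

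The rule is also the plan's only replacement provision, and it is keyed to toxicity evaluability. The primary endpoint depends on a biopsy at about six weeks, which the rule does not mention.

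**Working it through.** **1. Effect of an exclusion on a toxicity rate.** If *x* of *N* treated patients have the event and *k* are excluded, *e* of them with the event, the reported rate is (*x* − *e*)/(*N* − *k*). The counts below are assumed; the documents give no expected number of such departures.

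| Excluded | Of whom had the event | Reported rate |
|---|---|---|
| 0 | – | 11/20 = 55.0% |
| 1 | 1 | 10/19 = 52.6% |
| 1 | 0 | 11/19 = 57.9% |
| 2 | 2 | 9/18 = 50.0% |
| 2 | 1 | 10/18 = 55.6% |
| 2 | 0 | 11/18 = 61.1% |

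One exclusion moves the rate by 2.4 points down or 2.9 up. Two move it by 5.0 down to 6.1 up, and almost not at all if one of the two had the event.

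**2. The same from the reported side.** Suppose 18 patients per arm are reported after replacement, with *y* events. The all-treated rate is (*y* + *e*)/(18 + *k*). For scale, Section 3.2 cites 59% grade 3-4 related events for nivolumab plus ipilimumab (18 × 0.59 = 10.6, take 11). Section 3.3 cites 10.2% for nivolumab plus relatlimab (18 × 0.102 = 1.8, take 2).

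- Arm B, 11/18 = 61.1% reported. One excluded: 11/19 = 57.9% to 12/19 = 63.2%. Two excluded: 11/20 = 55.0% to 13/20 = 65.0%.
- Arm A, 2/18 = 11.1% reported. One excluded: 2/19 = 10.5% to 3/19 = 15.8%. Two excluded: 2/20 = 10.0% to 4/20 = 20.0%.

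In the arm with the low rate the error is lopsided: about 1 point of overstatement against up to about 9 of understatement.

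**3. Replacement window against biopsy timing.** Cycle 1 is 28 days in Arm A and 21 days in Arm B (synopsis). The biopsy falls on day 28 + 15 = 43 in Arm A and day 21 + 21 + 1 = 43 in Arm B, each with a window of 7 days either way. The replacement window therefore covers 28/42 = 67% of the time to biopsy in Arm A and 21/42 = 50% in Arm B. At no time does it cover a treatment-related discontinuation, or a failed or refused biopsy.

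**4. The plan's own figures.** For a two-sample t-test with 18 per arm, a difference of 1 SD and two-sided 0.05, there are 34 degrees of freedom and the noncentrality is 1/√(1/18 + 1/18) = 3. Power is 0.830, which reproduces the stated 83%. Enrolment is 36/0.90 = 40, also reproduced.

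With fewer evaluable pairs per arm, the same calculation gives 80.7% at 17, 78.1% at 16 and 75.3% at 15. If an arm closes at 18 enrolled and 10% lack a pair, 18 × 0.90 = 16.2 remain, so power is about 78%. If 40 are enrolled as 20 per arm (the split is assumed), 20 × 0.90 = 18 and the 83% stands.

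**The case against.** The rule is narrow. It applies only to unrelated departures in cycle 1, so patients who stop for toxicity, or for a reason that is not clear, stay evaluable. Those are the leavers who say most about tolerability. A reader might infer that every cycle 1 leaver is dropped; the text does not say so.

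A reader might also infer that early events vanish. They do not. Section 13.1 keeps collecting them, serious events are reported regardless of cause, and the data and safety monitoring committee reviews serious events quarterly (Section 15.3). What can be lost is their place in a summary percentage.

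It can further be said that Section 18 never states that the safety tables use the evaluable-for-toxicity set. That is true, so bias is a consequence of following 5.4 as written and not a demonstrated result. But 5.4 is the only text on who counts for toxicity, and leaving the safety population undefined does not override it.

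Finally, biopsy attrition is not ignored. Section 18.2 allows 10% dropout, each replacement refills a slot, and stopping treatment does not in itself rule out a biopsy. This stands. The difficulty is that the Section 2 accrual stop conflicts with the allowance.

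**Conclusion.** The point holds as a rule to correct, not as a proven bias. Section 5.4 removes some dosed patients from the toxicity evaluation by an open-label judgement made after dosing, and Sections 18.3 and 18.4 do not restore them. The direction is not fixed: dropping patients without events raises the rate, and dropping patients with events lowers it.

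The size is about 2 to 3 points for one exclusion from 11/20, and up to 5 or 6 points for two that go the same way. It would be tempting to put it at 5 to 6 points per patient, but that is one patient's weight in the denominator (1/20 to 1/18), not the effect of leaving one out. The event counts and the one or two exclusions per arm are assumptions.

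On the primary endpoint, the supported statement is that the cycle 1 rule does not by itself secure 18 evaluable pairs per arm. The stronger reading, that the biopsy endpoint is unprotected, is not supported given the 10% allowance. The figure of about 78% power applies only if accrual really stops at 18 enrolled per arm and about 10% lack a pair.

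**What to change.** 1. Amend Sections 5.4 and 18.3 so that every patient who receives at least one dose of any study drug stays in all safety summaries, whether or not the patient is replaced.
2. Report the number of replaced patients and the reasons, by arm.
3. Reconcile the 40 planned in Section 18.2 with the stop at 18 enrolled per arm in Section 2 and the 36 evaluable in Section 5.4, and say what evaluable means for the biopsy endpoint. Do this through the enrolment allowance. Replacing patients because the on-treatment biopsy is missing would select on a post-treatment outcome: those who progress, withdraw or have toxicity before day 43 would give way to those who reach biopsy.

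Items 1 and 2 cost only wording, because the adverse event data are already collected, and they alter no treatment rule. Item 3 needs no more than the 40 patients that Section 18.2 already plans. If 18 enrolled per arm is what is intended, the power statement should instead be restated for the number of pairs expected.
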